2.4.5 Analyses of safety data

2.4.5.1 Analyses of adverse events

Generalities

The primary focus of adverse event reporting will be on treatment-emergent adverse events. Pretreatment and posttreatment adverse events will be described separately.

If an adverse event date/time of onset (occurrence, worsening, or becoming serious) is incomplete, an imputation algorithm will be used to classify the adverse event as pretreatment, treatment-emergent, or posttreatment. The algorithm for imputing date/time of onset will be conservative and will classify an adverse event as treatment emergent unless there is definitive information to determine it is pretreatment or posttreatment. Details on classification of adverse events with missing or partial onset dates are provided in [Section 2.5.3](#).

Sorting within tables ensures the same presentation for the set of all adverse events within the observation period (pretreatment, treatment-emergent, and posttreatment). For that purpose, the table of all treatment-emergent adverse events presented by SOC and PT sorted by the internationally agreed SOC order and decreasing frequency of PTs within SOCs will define the presentation order for all other tables unless otherwise specified.

Analysis of all treatment-emergent adverse events

The following treatment-emergent adverse event summaries will be generated for the safety population.

- Overview of treatment-emergent adverse events, summarizing number (%) of patients with any
 - Treatment-emergent adverse event
 - Serious treatment-emergent adverse event
 - Treatment-emergent adverse event leading to death
 - Treatment-emergent adverse event leading to permanent treatment discontinuation
- All treatment-emergent adverse event by primary SOC, HLGT, HLT, and PT, showing number (%) of patients with at least 1 treatment-emergent adverse event sorted by the SOC internationally agreed order. The other levels (HLGT, HLT, PT) will be presented in alphabetical order

Analysis of all treatment emergent serious adverse event(s)

- All treatment-emergent serious adverse events by primary SOC, HLGT, HLT, and PT, showing the number (%) of patients with at least 1 serious treatment-emergent adverse event, sorted by the internationally agreed SOC order. The other levels (HLGT, HLT, PT) will be presented in alphabetical order

Analysis of all treatment-emergent adverse event(s) leading to permanent treatment discontinuation

- All treatment-emergent adverse events leading to treatment discontinuation, by primary SOC, HLG, HLT, and PT, showing the number (%) of patients sorted by the internationally agreed SOC order. The other levels (HLG, HLT, PT) will be presented in alphabetical order

Analysis of all treatment-emergent adverse event(s) leading to treatment discontinuation

- All treatment-emergent adverse events leading to treatment discontinuation, by primary SOC, HLG, HLT, and PT, showing the number (%) of patients sorted by the internationally agreed SOC order. The other levels (HLG, HLT, PT) will be presented in alphabetical order

Analysis of injection site reactions and hypersensitivity reactions

- The number and percentage of patients experiencing injection site reactions and hypersensitivity reactions will be summarized separately.

2.4.5.2 Deaths

The following summaries of deaths will be generated for the safety population.

- Number (%) of patients who died by study period (on-study, on-treatment, post-study)
- Deaths in nonrandomized patients or randomized but not treated patients

2.4.5.3 Analyses of hypoglycemia variables

Hypoglycemia analyses described in Section 2.4.4.2 will be repeated based on Safety Population.

The incidence and rate (nocturnal or 24 hours) of all hypoglycemic events will be analyzed for the hypoglycemia categories of severe, documented symptomatic, asymptomatic, probable and relative, as defined in the publication of the ADA Workgroup on Hypoglycemia, 2015.

The incidence (proportion of patients with any nocturnal symptomatic hypoglycemia events) will be analyzed using logistic regression, adjusting for randomization strata and other baseline characteristics (duration of diabetes, baseline BMI and age) if the model permits.

The risk ratio (RR) of hypoglycemia of Toujeo versus Lantus will be assessed by a log-binomial regression model adjusting for randomization strata and other baseline characteristics (duration of diabetes, baseline BMI and age) if the model permits.

2.4.5.4 Analyses of electrocardiogram variables

Not applicable.

2.4.6 Analyses of pharmacokinetic and pharmacodynamic variables

Not applicable.

2.4.7 Analyses of quality of life/health economics variables

Not applicable.

2.5 DATA HANDLING CONVENTIONS

2.5.1 General conventions

The following formulas will be used for computation of parameters.

Reference day

The reference day for the calculation of extent of exposure, time to onset and relative days is the day of the first administration of open-label IMP, denoted as Day 1.

Demographic formulas

Body Mass Index (kg/m²)= (Weight in kg) / (Height in meters)²

Disease characteristics formulas

Diabetes duration of (years) will be calculated as follows
= (Date of informed consent – Date of diagnosis of diabetes + 1)/365.25

Age at diagnosis of diabetes (years) will be calculated as follows
= (Date [MM-YYYY] of diagnosis of diabetes – date [MM-YYYY] of birth +1) /365.25.

In case of unavailable date of birth, only the year of the date of diabetes diagnosis and the year of the date of birth (retrieve using the age recorded at screening) will be considered in the age at diagnosis of diabetes calculation.

2.5.2 Data handling conventions for secondary efficacy variables

Fasting condition

FPG measurement not collecting in fasting condition will not be used in the analyses.

Invalid laboratory data

HbA1c or FPG measurements flagged as invalid by the laboratory will not be used in the analyses.

2.5.3 Missing data

For categorical variables, patients with missing data are not included in calculations of percentages unless otherwise specified. When relevant, the number of patients with missing data is presented.

Handling of CGM measurements outside detection range

CGM blood glucose values below the lower limit and above upper limit of detection range will be set to the lower and upper limits of detection, respectively, for the CGM parameter derivation.

Handling of computation of treatment duration if investigational medicinal product end of treatment date is missing

For the calculation of the treatment duration, the date of the last dose of IMP is equal to the date of last administration reported on the end-of-treatment case report form page. If this date is missing, the exposure duration should be left as missing.

The last dose intake should be clearly identified in the case report form and should not be approximated by the last returned package date.

Handling of missing baseline and end of treatment IMP doses

For baseline and end of treatment IMP dose calculations, if the dose on the date of randomization or the dose at the end of treatment is not available, the last available dose within 2 days prior to randomization and the last available dose within 2 days prior to the end of the treatment will be used.

Handling of missing IMP injection time for the purpose of CGM parameter calculation

For the calculation of secondary efficacy end point, percentage time glucose concentrations obtained by CGM within target range of 70-140 mg/dL (3.9–7.8 mmol/L) during the last 4 hours of CGM data collection prior to next day basal insulin injection, if the injection time of the IMP is missing, the injection time from the prior day will be used as it is assumed that IMP should be injected at the same time in the morning.

Handling of medication missing/partial dates

No imputation of medication start/end dates or times will be performed. If a medication date or time is missing or partially missing and it cannot be determined whether it was taken prior or concomitantly, it will be considered a prior, concomitant, and posttreatment medication.

Handling partial date of birth:

For calculation age, missing birth day is assumed as the 15 of the month. If month is missing, the age will be calculated as Year of date of consent- Year of birth.

Handling of partial date of diagnosis of Type 1 diabetes

Partial date of diagnosis of Type 1 diabetes will be imputed to calculate the duration of diabetes.

In order to calculate:

- Duration of diabetes (year)
- Age at diagnosis of diabetes (year)

If only day is missing, only month and year will be used. If month is missing, only year will be used in calculation.

Handling of potentially clinically significant abnormalities

If a patient has a missing baseline he/she will be grouped in the category “normal/missing at baseline.”

Handling of missing hypoglycemia data

To determine nocturnal symptomatic hypoglycemia, if the time of hypoglycemia is not captured, the time of BG collected from the hypoglycemia e-CRF will be used. If more than one hypoglycemia event is reported, the earliest time stamp and lowest BG level, requiring assistance will be used to determine the hypoglycemia event type.

Handling of more than one hypoglycemic events within 30 minutes interval

If there are more than hypoglycemia events within 30 minutes interval, the one with the lowest glucose level will be used.

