9.3.1 Hypoglycemia

9.3.1.1 Hypoglycemia classification

Hypoglycemia events will be categorized [5] as follows:

Severe hypoglycemia

Severe hypoglycemia is an event requiring assistance of another person to actively administer carbohydrate, glucagon, or other resuscitative actions. These episodes may be associated with sufficient neuroglycopenia to induce seizure, unconsciousness or coma. Plasma glucose measurements may not be available during such an event, but neurological recovery attributable to the restoration of plasma glucose to normal is considered sufficient evidence that the event was induced by a low plasma glucose concentration.

The definition of severe symptomatic hypoglycemia includes all episodes in which neurological impairment was severe enough to prevent self-treatment and which were thus thought to place patients at risk for injury to themselves or others.

Note that "requiring assistance of another person" means that the patient could not help himself or herself to treat the hypoglycemia. Assisting a patient out of kindness, when assistance is not required, should not be considered a "requires assistance" incident.

Any hypoglycemic event which leads to unconsciousness, coma, or seizure must be reported as an SAE. In addition, any hypoglycemic event, which at Investigator discretion, qualifies as serious adverse event must also be reported as an SAE.

• Documented symptomatic hypoglycemia

Documented symptomatic hypoglycemia is an event during which typical symptoms of hypoglycemia accompanied by a measured plasma glucose concentration of \leq 70 mg/dL (3.9 mmol/L).

In addition, hypoglycemia episodes with plasma glucose of < 54 mg/dL (3.0 mmol/L) will also be analyzed.

Clinical symptoms that are considered to result from a hypoglycemic episode are, eg, increased sweating, nervousness, asthenia/weakness, tremor, dizziness, increased appetite, palpitations, headache, sleep disorder, confusion, seizures, unconsciousness, or coma.

Asymptomatic hypoglycemia

Asymptomatic hypoglycemia is an event not accompanied by typical symptoms of hypoglycemia but with a measured plasma glucose concentration less than or equal to 70 mg/dL (3.9 mmol/L).

In addition, hypoglycemia episodes with plasma glucose of < 54 mg/dL (3.0 mmol/L) will be analyzed.

• Probable symptomatic hypoglycemia

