Pre-injection SMPG: Within 30 min prior to injection of Toujeo or Lantus before breakfast: on the day of the first injection of the IMP (Day 1) and daily until uptitration has been completed and fasting pre-breakfast SMPG is stable in the target range, and then, at least 5 days per week before each onsite visit.

5-point SMPG profiles

Before breakfast (pre-injection after randomization), before lunch, before dinner and 2-hours post one of any meals and at bedtime (the post-meal SMPG may be done 2 hours after the patient's main meal, e.g. lunch or dinner, or as per investigator's instruction) at least 5 days per week during the week before the baseline until the fasting and postprandial glucose targets have been reached. However, it is mandatory to perform at least 3 days during the week prior to the visits that the SMPG data will be collected in the eCRF (Section 10.2.3.2).

7-point SMPG profiles

Before (pre-injection after randomization) and 2 hours after breakfast; before and 2 hours after lunch; before and 2 hours after dinner and at bedtime: at least one day in the week before the baseline visit and before Visit 15 and 19.

SMPG during symptomatic hypoglycemia

Whenever the patients feel hypoglycemic symptoms, plasma glucose should be measured by the patient (or others, if applicable), if possible. Patients should be instructed to measure plasma glucose levels prior to carbohydrate intake/administration of glucose whenever symptomatic hypoglycemia is suspected, unless safety considerations necessitate immediate carbohydrate/glucose rescue prior to confirmation with the SMPG.

Patients have to document hypoglycemic events appropriately in their diaries and to contact the investigator as soon as possible following severe events for review and for decision on any necessary actions to be taken.

All hypoglycemia episodes will be documented on the "hypoglycemia specific form" in the e-CRF. This includes all symptomatic hypoglycemia events and asymptomatic hypoglycemia.

Hypoglycemia events fulfilling the criteria of a SAE will be documented on the SAE form in the e-CRF.

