2.1.3.2 Secondary efficacy endpoint(s)

The main secondary efficacy endpoints include:

- Incidence and rate of nocturnal symptomatic hypoglycemia, defined as an event with typical symptoms of hypoglycemia accompanied by SMPG ≤ 70 mg/dL (3.9 mmol/L) that occurs between 00:00 and 05:59 hours,
- The mean change of each participant's glucose level during the last four hours of CGM data collection prior to next day's basal insulin injection ([1](#)),
- Percentage (%) of time glucose concentrations obtained by CGM within target range of 70-140 mg/dL (3.9–7.8 mmol/L) during the last 4 hours of CGM data collection prior to next day basal insulin injection,
- Total, within day and between day CV% in glucose values obtained from CGM.

Testing strategy of the six main secondary endpoints can be found in [Section 2.4.4.3](#).

The other secondary efficacy endpoints include:

- Frequency and distribution (nocturnal or 24 hours) of all hypoglycemia events analyzed by hypoglycemia categories (severe, documented symptomatic, asymptomatic, probable and relative) as defined in the publication ADA Workgroup on Hypoglycemia, 2015 (see [Appendix A](#)),
- Additional CGM endpoints (data obtained at Week 16):
 - Percentage (%) of time glucose concentrations within the target range of 70-140 mg/dL (3.9–7.8 mmol/L), analyses on all-time (24 hours) CGM data.
 - Percentage (%) of time in hypoglycemia defined as percentage time with glucose concentrations < 70 mg/dL (3.9 mmol/L) and < 54 mg/dL (3 mmol/L), analyses on both all-time (24 hours) and nocturnal (00:00–05:59 h) CGM data
 - Percentage (%) of time in hypoglycemia defined as percentage time with glucose > 140 mg/dL (7.8 mmol/L), > 180 mg/dL (10 mmol/L) and > 250 mg/dL (13.9 mmol/l), analyses on both all-time (24 hours) and nocturnal (00:00–05:59 h) CGM data.

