2.1.3.2.1 Hypoglycemia

2.1.3.2.1.1 Hypoglycemia classification

Hypoglycemia observation periods

- **Pre-treatment hypoglycemia events** are events that occur during the pre-treatment period
- **Treatment-emergent hypoglycemia events** are events that occur during the on-treatment period
- **Post-treatment hypoglycemia events** are events that occur during the post-treatment period

Hypoglycemia events will be categorized as defined in [Appendix A](#). The glucose values used to classify hypoglycemia events are from the hypoglycemia e-CRF rather than the glucose values from CGM or central laboratory.

The incidence (proportion of patients with any hypoglycemia events) and the rate (number of events per patient year of exposure) will be assessed during each safety observation period for each hypoglycemia category.

In case of some classification items are missing (i.e. assistance required or not, presence of symptom, glycemic values, use of countermeasure) to determine hypoglycemia classification (see Section 2.5.3) the following categories will be presented.

- Not classified – non severe
- Not classified – severity unknown

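### The SAP's 30-minute hypoglycemia rule selects a record on glucose alone, so it can change an episode's severity, symptom or nocturnal label, and it conflicts with the paragraph before it

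*SAP*

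**What the plan says.** SAP Section 2.5.3 ends with two instructions for more than one hypoglycemia record.

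- Under the heading on missing hypoglycemia data: "If more than one hypoglycemia event is reported, the earliest time stamp and lowest BG level, requiring assistance will be used" to set the event type. No time window is given and symptoms are not mentioned.
- Directly after, under its own heading: "If there are more than hypoglycemia events within 30 minutes interval, the one with the lowest glucose level will be used". A word has dropped out, but the heading makes clear that more than one event is meant.

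The second instruction is repeated in SAP Section 1.6 as the third declared modification. The protocol contains no such rule.

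The definitions that these instructions feed are as follows.

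- Severe events (Protocol Section 9.3.1.1): "Severe hypoglycemia is an event requiring assistance of another person to actively administer carbohydrate, glucagon, or other resuscitative actions". For these events the same section adds: "Plasma glucose measurements may not be available during such an event".
- Nocturnal symptomatic events (SAP Section 2.1.3.2): symptoms, an SMPG of 70 mg/dL or less, and an event "that occurs between 00:00 and 05:59 hours".
- The hypoglycemia form (Protocol Section 10.2.3.1): "This includes all symptomatic hypoglycemia events and asymptomatic hypoglycemia".
- The glucose source (SAP Section 2.1.3.2.1): "The glucose values used to classify hypoglycemia events are from the hypoglycemia e-CRF rather than the glucose values from CGM or central laboratory".

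**The concern.** The record that survives the 30-minute rule carries its own assistance flag, symptom flag and time into the analysis. The rule picks that record on glucose, which determines none of the three. An episode can therefore be labelled by a record that does not represent it.

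The labels matter. In SAP Section 2.4.4.3 the incidence and the rate of nocturnal symptomatic hypoglycemia are tests 1 and 2 after the primary, and tests 3 to 7 depend on both. SAP Section 1.3 calls the rate the key secondary endpoint and claims at least 80% power at a rate ratio of 0.86. SAP Section 2.4.5.3 repeats the hypoglycemia analyses on the safety population by category, including severe.

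Two programmers could each follow Section 2.5.3 faithfully and obtain different event counts. In an open-label trial that choice should be fixed on paper before database lock.

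**Working it through.** The documents attach no figure to this rule, so the check is one of logic. Both instructions were applied to six constructed pairs of records, each 20 minutes apart, and the results were classified by the definitions above. The preceding paragraph was read as earliest time, lowest glucose, and severe if assistance was required. Glucose is in mg/dL.

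| Pair | Records | 30-minute rule | Preceding paragraph |
|---|---|---|---|
| A | 02:00 severe, no glucose; 02:20 self-treated symptomatic 62 | Undefined; non-severe if blanks are skipped | Severe |
| B | 02:00 severe 55; 02:20 self-treated symptomatic 50 | Non-severe (50 < 55) | Severe |
| C | 03:00 symptomatic 66; 03:20 asymptomatic 60 | Asymptomatic: nocturnal symptomatic event lost | Silent on symptoms |
| D | 05:45 symptomatic 66; 06:05 symptomatic 60 | Daytime: nocturnal event lost | Nocturnal |
| E | 23:50 symptomatic 66; 00:10 symptomatic 60 | Nocturnal: nocturnal event gained | Daytime |
| F | 02:00 symptomatic 60; 02:20 symptomatic 66 | Nocturnal symptomatic | Same |

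Reading across:

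1. The two instructions agree when the lowest reading is also the earliest and assistance does not differ (F). They conflict on assistance (B, and A if blanks are skipped) and on time (D, E).
2. C is a loss under the 30-minute rule but not a contradiction, because the preceding paragraph does not mention symptoms.
3. In A (blanks skipped) and B only the severe label is lost. The retained record still meets the nocturnal symptomatic definition. The tested endpoints change in C, D and E.
4. D loses a nocturnal event and E gains one, so the direction is not fixed.
5. Incidence counts patients with any event, so it changes only when the affected event is the one that decides the patient's status. The rate changes with every affected event.

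**Scale only, not an estimate.** The 80% power in SAP Section 1.3 cannot be reproduced, because no Lantus rate or dispersion is given. Without overdispersion, a rate ratio of 0.86 needs E = 4 × (1.96 + 0.8416)² / (ln 0.86)² ≈ 1381 events in total. If a fraction q of events were lost equally in both arms (an assumption), power would be Φ(|ln 0.86| × √(E(1 − q)/4) − 1.96):

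| q | 0% | 1% | 2% | 5% | 10% |
|---|---|---|---|---|---|
| Power | 80.0% | 79.6% | 79.2% | 78.0% | 75.8% |

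Nothing in the documents says where in this range q would lie, and E shows that events can also be gained.

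**The case against.** The best defence is that the paragraphs do different jobs. The first sits under a missing-data heading and sets the event type, including assistance. The second only collapses near-duplicates. Read together, severe status is kept. Part of this stands: the preceding paragraph does name assistance, so the SAP does not ignore severity altogether. But its sentence carries no missing-data condition, nothing available ranks the two instructions, and this reading helps neither C nor the time conflict in D and E.

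A reader might infer more than the documents support:

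- *That every severe record without glucose is deleted when it has a companion record.* The SAP does not say how a blank is ranked, or whether the rule applies to it. SAP Section 2.1.3.2.1.1 also keeps events with missing classification items in two unclassified groups. The handling is undefined, which is not the same as certain deletion.
- *That displaced severe events leave the key secondary endpoint.* The self-treated nocturnal reading in A or B still qualifies.
- *That the rule only loses events, or favors one arm.* E is a gain, and nothing suggests that the rule treats the arms differently.
- *That a percentage of lost events can be stated.* The frequency of paired records is not given.

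Two limits remain. The text of SAP Appendix A, which holds the classification, was not available and could state a priority. The e-CRF form was not available either, so it is unknown whether repeat readings become separate records. SAE reporting of hypoglycemia runs on its own form (Protocol Sections 9.3.1.1 and 10.2.3.1) and is unaffected.

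**Conclusion.** The concern holds as a defect in a stated rule, not merely as missing detail. Taken literally, the 30-minute rule conflicts with the severe definition in B and with the nocturnal symptomatic definition in C and D. It also conflicts with the preceding paragraph whenever records differ in time or assistance. The treatment of a severe record without glucose is left open.

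No numerical effect is claimed. The number of affected episodes is unknown, the net direction is not fixed, and the power figures above rest on assumed losses. The conclusion assumes that Appendix A does not already rank the instructions. The point deserves correction because it touches the first two tests after the primary and the severe counts, and because it is cheap to put right.

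**What to change.** Before database lock, replace both sentences in SAP Section 2.5.3, and item 3 of SAP Section 1.6, with one rule:

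1. Classify each record by the protocol definitions.
2. Group all records within 30 minutes of the first record into one episode.
3. Give the episode the highest category present: severe if any record required assistance, with or without glucose; then documented symptomatic; then the other categories in a stated order.
4. Report the lowest available glucose.
5. Use one pre-stated time stamp, for example the earliest, for the nocturnal label.

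Classifying before grouping matters. Pooling symptoms from one record with glucose from another could turn a relative event (symptoms, 74 mg/dL) and an asymptomatic 68 mg/dL into a documented symptomatic event that no record shows. The text should also say whether an episode labelled severe counts toward the nocturnal symptomatic endpoint when one of its records meets that definition. The endpoint definition does not exclude severe events.

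The cost is a short SAP edit and a small change to the event-derivation program, with no new data. The downside is that a few episodes near midnight or 06:00 change label. With the earliest time stamp, for example, the 23:50 and 00:10 pair becomes daytime.
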